**\*\*\* Amendment \*\*\***

Amendment (1. Complete this one-page form, 2. Update the sections of your protocol that you are requesting to amend, 3. Electronically "sign" your application by clicking the check box on the Obligations page, 4. Remember to click "Submit Form" so that the IRB administrators receive your request.)

1. **Summarize the proposed changes to the protocol in lay terms.**

Change of principal investigator to [name].

Proceed to the appropriate section(s) of the protocol and make your changes.

**IMPORTANT NOTE ON AMENDING ATTACHED DOCUMENTS:** If you are requesting to amend a file that has been previously attached and approved, you **MUST:** 1. Delete the file that is currently attached, 2. Browse on your computer, and 3. Upload the revised file that you are requesting to use.

2. **Indicate level of risk involved with the changes proposed.**

(If level of risk has changed, please update the section 'Risks' in the protocol information.)

No Change

Approval Includes

3. **List of sections (and questions) that have been changed/modified**

---

**\*\*\* Subject Population \*\*\***

**Subject Population(s) Checklist**

Â Select All That Apply - Note that this is your Targeted Population :

- X Adult Volunteers
- Decisionally Challenged
- X Elderly
- Employees
- Fetuses
- Long-Term Patients
- Mentally Disabled
- Minors (under 18)
- Pregnant Women
- Prisoners
- Soldiers
- X Students
- Other (i.e., non-English Speaking or any population that is not specified above)

-----  
**\*\*\* Study Location \*\*\***

**Study Location(s) Checklist**

Select All That Apply - NOTE: Check "Other" and input text: 1.) If your study location is not listed, or 2.) If you would like to list details of your already-checked location (e.g., specific school within a school district)

- Aims Community College
- Colorado Department of Public Health & Environment
- X Colorado State University
- Colorado State University - Pueblo Campus
- Denver Public Schools
- Greeley/Evans School District
- Poudre School District
- University of Colorado Health - North (Formerly -Poudre Valley Health System - PVHS)
- Rocky Mountain National Park
- Thompson School District
- University of Colorado - Boulder
- University of Colorado - Colorado Springs
- University of Colorado - Denver
- University of Colorado Health Sciences Center
- University of Northern Colorado
- Other (In the box below, list your study location if not checked above. You may also list details of your already-checked location (e.g., specific school within a school district).

-----  
**\*\*\* General Checklist \*\*\***

## General Checklist

Select All That Apply :

X Proposed Start Date (cannot be before IRB approval):

X Sponsored Project (Check if you will be funded OR if you have or plan to submit a grant application in association with this protocol)

NSF Sponsored (Please upload mandatory Data Management Plan in the Attachment section)

X FDA or EPA-regulated research. Please contact the CSU Quality Assurance Manager, [name], at [contact] to determine if your study is under Good Laboratory, Good Clinical, or Good Manufacturing Practices (GLP, GCP, GMP).

Training Grant

X Clinical Trial. To register your trial on Clinicaltrials.gov, please contact [name], CSU Quality Assurance Manager and Clinical Trails Administrator at: [contact].

Project is associated with the Colorado School of Public Health - CSPH(faculty and/or student)

Cooperating/Collaborating Institution(s) Institution where recruitment will occur OR Institution where Collaborating PI will conduct associated research.

### Interview

Questionnaire/Survey

X Subjects will be compensated for participation

Thesis or Dissertation Project

X  $\Delta\Delta$  Radioisotopes/radiation-producing machines, even if standard of care. Please contact [name], Radiation Safety Officer for questions related to use of all radiation-producing machine: [contact]; [contact]. Upload your radiation-use approval (if available) or your Radiation Safety Training certificate in the attachment section.

X Human blood, cells, tissues, or body fluids. You will need to obtain IBC approval if you check this box. For information regarding IBC approval, contact [name], IBC Coordinator: [contact]

Tissues to be stored for future research projects

Tissues to be sent out of this institution as part of a research agreement

Human Embryos. You will need to obtain IBC approval if you check this box. For information regarding IBC approval, contact [name], IBC Coordinator: [contact]

Human Embryonic Cells? Provide NIH Code Number(s) or state that no federal funding will be used to support this research. You may need to obtain IBC approval if you check this box. For information regarding IBC approval, contact [name], IBC Coordinator: [contact]

Use of Patient-related equipment? If Yes, specify what equipment is being used.

Medical equipment used for human patients/subjects also used on animals. For questions regarding animal use approval, contact [name], IACUC Senior Coordinator: [name]

Protocol involves studying potentially addicting drugs. For questions regarding approval for possession of controlled substances, contact [name], DRC Coordinator: [name]; [contact].

Investigational drugs, reagents, or chemicals (IND)

X Commercially available drugs, reagents, or other chemicals administered to subjects (even if they are not being studied)

X Investigational Device (IDE)

Cancer Subjects (e.g., clinical trials, behavior/prevention) or Cancer Tissues (e.g., blood, cells, body fluids). You may need to obtain IBC approval if you check this box. For information regarding IBC approval, contact [name], IBC Coordinator: [contact]

Other (clarify in text box to the right)

-----  
**\*\*\* Funding \*\*\***

Please complete this section if: 1. This protocol will be funded, 2. You have submitted or will submit a grant application associated with this protocol. Please be sure to input your PASS/SP1 number to assist Sponsored Programs in setting up an account for your funds.

If this protocol is funded by the NIH or NSF, or will lead to the regulatory involvement of the FDA or EPA, please be certain you are cognizant of any specific regulatory requirements for data acquisition, storage, retention and sharing, as well as research expenditure allowability, with regard to this IRB protocol.

**Funding Checklist**

NONE

NOTE: Applicable Federal Grant Application, including competing renewals, must be attached in the Attachment Section (#16). Applicable investigator's brochure and sponsor's protocol must also be attached in section #16 for all industry-sponsored clinical trials.

**Funding - Grants/Contracts**

Funding Administered By	UNIVERSITY
CSU PASS #	121860
Sponsor's ID # (If known)	
Funded By	Other Dairy Management Inc.
Principal Investigator	[name]
Grant/Contract Title if different from Protocol Title	Milk Protein Feeding After Aerobic Exercise in Older Adults with Pre-Diabetes Taking the Biguanide Metformin
	For Federal projects, are contents of this protocol the same as described in Federal proposal application?
N	Is this an Umbrella protocol?
N	Is this protocol under an Umbrella protocol?

Funding Administered By	UNIVERSITY
CSU PASS #	
Sponsor's ID # (If known)	
Funded By	Other Dexcom Inc.
Principal Investigator	
Grant/Contract Title if different from Protocol Title	
	For Federal projects, are contents of this protocol the same as described in Federal proposal application?
	Is this an Umbrella protocol?
	Is this protocol under an Umbrella protocol?

**Funding - Fellowships**

## Funding - Other

Gift Funding

Dept. Funding

Other Funding

---

### **\* \* \* Expedited Paragraphs \* \* \***

**PLEASE READ:** This online application is for projects that will be reviewed by the IRB via the expedite or full-board review process. The criteria for expedited review are listed below. Review and check what expedite criteria is/are appropriate for your project. **NOTE:** If your research involves or may involve greater than minimal risk, an element of deception, or is FDA-regulated research, do NOT check any of the expedited criteria listed below. Your protocol will then be reviewed by the full-board at their next regularly scheduled meeting. If your project meets the exempt criteria, please submit your exempt application via email to: [RICRO\\[contact]](mailto:[contact]). Information regarding exempt applications can be found here: <http://ricro.colostate.edu/IRB/ExemptReview.html>

#### **Expedite Criteria:**

1. **Clinical studies of drugs and medical devices only when condition (a) or (b) is met.**
  - a) **Research on drugs for which an investigational new drug application (21 CFR Part 31,32) is not required. (Note: Research on marketed drugs that significantly increases the risks or decreases the acceptability of the risks associated with the use of the product is not eligible for expedited review.)**
  - b) **Research on medical devices for which**
    - i) **An investigational device exemption application (21 CFR Part 812) is not required; or**
    - ii) **The medical device is cleared/approved for marketing and the medical device is being used in accordance with its cleared/approved labeling.**
2. **Collection of blood samples by finger stick, heel stick, ear stick, or venipuncture as follows:**
  - a) **From healthy, nonpregnant adults who weigh at least 110 pounds. For these subjects, the amounts drawn may not exceed 550 ml in an 8- week period and collection may not occur more frequently than 2 times per week; or**
  - b) **From other adults and children, considering the age, weight, and health of the subjects, the collection procedure, the amount of blood to be collected, and the frequency with which it will be collected. For these subjects, the amount drawn may not exceed the lesser of 50 ml or 3 ml per kg in an 8-week period and collection may not occur more frequently than 2 times per week.**
3. **Prospective collection of biological specimens for research purposes by non-invasive means.**
4. **Collection of data through non-invasive procedures (not involving general anesthesia or sedation) routinely employed in clinical practice, excluding procedures involving x-rays or microwaves. Where**

medical devices are employed, they must be cleared/approved for marketing. (Studies intended to evaluate the safety and effectiveness of the medical device are not generally eligible for expedited review, including studies of cleared medical devices for new indications.)

**Examples:**

- a) Physical sensors that are applied either to the surface of the body or at a distance and do not involve input of significant amounts of energy into the subject or an invasion of the subject's privacy;
  - b) Weighing or testing sensory acuity;
  - c) Magnetic resonance imaging;
  - d) Electrocardiography, electroencephalography, thermography, detection of naturally occurring radioactivity, electroretinography, ultrasound, diagnostic infrared imaging, doppler blood flow, and echocardiography;
  - e) Moderate exercise, muscular strength testing, body composition assessment, and flexibility testing where appropriate given the age, weight, and health of the individual.
5. Research involving materials (data, documents, records, or specimens) that have been collected, or will be collected solely for nonresearch purposes (such as medical treatment or diagnosis). (NOTE: Some research in this paragraph may be exempt from the HHS regulations for the protection of human subjects. 45 CFR 46.101(b)(4). This listing refers only to research that is not exempt.)
6. Collection of data from voice, video, digital, or image recordings made for research purposes.
7. Research on individual or group characteristics or behavior(including, but not limited to, research on perception, cognition, motivation, identity, language, communication, cultural beliefs or practices, and social behavior) or research employing survey, interview, oral history, focus group, program evaluation, human factors evaluation, or quality assurance methodologies. (NOTE: Some research in this category may be exempt from the HHS regulations for the protection of human subjects. 45 CFR 46.101(b)(2) and (b)(3). This listing refers only to research that is not exempt.)

-----  
**\*\*\* Purpose, Study Procedures, Background \*\*\***

Original Protocol Number (e.g., 07-226H)

**Title (Please indicate if the protocol title is different from the proposal title)**

Milk protein feeding after aerobic exercise in older adults with pre-diabetes taking the biguanide metformin

Complete Sections 1 - 16. Specify N/A as appropriate. Do not leave any required sections blank.

**1. Purpose of the study**

- a) Provide a brief lay summary of the project in <200 words. The lay summary should be readily understandable to the general public, and is, for example, what would be released to a newspaper if requested.

We propose that post-exercise milk protein feeding will enhance the mitochondrial protein synthesis (biogenesis) response to an exercise-training program. In addition, we propose that this stimulatory effect of protein feeding will overcome the potential blunting effect of metformin on exercise responses. We will investigate these outcomes over a 12-week exercise-training program in older adults with pre-diabetes with or without metformin treatment.

Sub-study:

- 1. CGM in Individuals with prediabetes undergoing an exercise-training program with or without Metformin.
- 2. CGM in healthy control individuals to compare to individuals with prediabetes.

**b) What does the Investigator(s) hope to learn from the study?**

We hope to:

- a) provide the first evidence that post-exercise milk protein supplementation is effective in diseased population (i.e., older adults with pre-diabetes) and those on medications (i.e., metformin).
- b) demonstrate that the potential inhibitory effects of metformin on aerobic exercise adaptations can be opposed by milk protein feeding.

Sub-study

1. Glucose Profiles via CGM in pre diabetic individuals before, during and after the intervention (i.e., aerobic exercise training with or without metformin with post-exercise carbohydrate or carbohydrate+protein feeding as listed below in 2a).
- 2: Glucose profiles via CGM in healthy individuals. Healthy individuals will complete baseline procedures but will not complete an intervention.

**c) Proposed Start Date (may not precede IRB approval date):**

August 1, 2015

2.

Study Procedures (If this is a student project, the methods section of the thesis or dissertation proposal must be attached in section #16 - Attachment section.)

**a) In lay language, describe all the procedures, from screening through end-of-study, that the human subject must undergo in the research project, including study visits, drug treatments, randomization and the procedures that are part of standard of care. Please note: Do NOT respond "See Attachment Section." If you would like to add tables, charts, etc., attach those files in the Attachment section (#16).**

Study Overview:

Pre-diabetic and healthy participants will first undergo a medical questionnaire, resting ECG, graded exercise test with ECG and assessment of VO2max, anthropometric measurement (height, weight and body composition by DEXA scanning), an oral glucose tolerance test (OGTT), and a muscle biopsy.

Prediabetic participants will be screened to eliminate those lactose intolerant, medications known to affect the primary outcomes, medications or recent procedures contraindicated with metformin or not pre-diabetic. Subjects who meet these criteria will be randomized so that subject characteristics are matched between groups, while the study team and participants will remain blinded to treatment (i.e., randomized, double-blind study design). Subjects will be assigned to exercise + carbohydrate + placebo, exercise + protein + placebo, exercise + carbohydrate + metformin, or exercise + protein + metformin.

A minimum of two days apart from the VO2max test, skeletal muscle will be sampled from pre-diabetic and healthy participants. During these visits, pre-diabetic subjects will have the option to participate in a study to test the impact of one counseling session on physical activity after completion of the exercise training and to identify individual, socio-cultural and environmental determinants of physical activity 12 weeks after the end of the exercise intervention. If the subjects wish to participate they will complete questionnaires to measure sociodemographic information, physical activity, self-efficacy, planning, self-regulation and outcome expectancy of exercise, and perceptions of neighborhood support at baseline, completion of exercise training and 12 weeks after the exercise training.

Pre diabetic and healthy participants will also have the option to participate in a study to wear a Dexcom generation 6 (G6) continuous glucose monitor (CGM) to measure glucose values every 5 minutes. Healthy participants will wear the device once for up to 10 consecutive days. Pre-diabetic participants will wear the device for up to 10-consecutive days at three different time points: before, during and after the 12-week exercise intervention for a total of 30 days wearing the CGM. The Dexcom G6 CGM is for investigational use only and is not FDA approved. The G6 is modeled after commercially available, FDA approved CGM devices. The differences between the G6 and commercially available devices are a reduced calibration scheme, meaning less finger stick blood glucose measurements for calibration; a longer wear for up to 10 days for the G6 vs. 7 days for commercially available product. Last, commercially available devices could give false high glucose readings if individuals took acetaminophen. The G6 sensor contains updated sensor technology aimed to block the interference of acetaminophen.

After randomization into placebo or metformin groups, the pre-diabetic subjects will begin a 12-wk exercise

intervention consisting of 3 days per week of aerobic exercise training with post-exercise consumption of a 20 gram protein beverage or isocaloric carbohydrate beverage. We have completed this supplementation protocol in previous studies and a currently ongoing investigation.

At the 8-wk time point, pre-diabetic subjects will begin the daily consumption of heavy water (D2O) for the assessment of mitochondrial and individual protein synthesis. At the completion of the training period, the pre-diabetic subjects will repeat all assessments performed prior to training including the DEXA, VO2max, OGTT and muscle sample. Muscle samples obtained pre- and post-training will be used to evaluate mitochondrial function using high-resolution respirometry, western blot analysis, and stable isotope incorporation (post only).

Healthy participants will complete the medical history questionnaire, resting ECG, graded exercise testing (ECG and VO2max), DEXA, OGTT, CGM, and muscle biopsy.

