**Exercise Training:** The exercise-training program will be performed within the facilities for the Noon Hour Fitness Program at CSU according to our previously published procedures in older individuals. Exercise will be performed on a treadmill, stationary bicycle, or elliptical and include warm-up (15 min at a heart rate corresponding to 60% of max ) and workout stages (30 min, progression from 65 to 85% of max heart rate by wk 5). The participants will wear heart rate monitors to ensure proper heart rate ranges and the speed, grade or resistance of equipment will be changed to maintain heart rate at the specified percentage of max HR. A CPR trained technician will supervise each exercise session to monitor adherence to the exercise prescription and ensure subject safety. The drinks will be consumed immediately after exercise under supervision.

**Nutritional Intervention:** Subjects will consume either a protein-carbohydrate or carbohydrate drink with a consistency and temperature similar to a smoothie or milk shake immediately after each exercise bout. The protein-carbohydrate drink will be greek yogurt+fruit (~300 kcal, 63g carbohydrate, 20g protein, 1g fat) and the carbohydrate will be fruit (~300 kcal, 82g carbohydrate, 2g protein and 1g fat).

**Metformin and Placebo:** We use a titration dosing protocol in which the amount of metformin starts at 500 mg/day in week 1 and increases by 500 mg/day/week until reaching 2000 mg/day by week 4. 2000 mg/day is the standard clinical dose and used previously by the investigative team. The titration dosing scheme and taking metformin/placebo with meals will help reduce the most common side effects (i.e., gastrointestinal discomfort). If participants experience gastrointestinal discomfort, the dose will be lowered to 1500 mg/day. If participants have a body weight of 75 kg or less the maximal dose will be 1500 mg/day to decrease the risk of gastrointestinal discomfort.

**Stable Isotope Labeling:** The subjects will consume D2O (70%; Cambridge Isotope Laboratories, Andover

MA, USA) during the last four-week period of the 12 week intervention. D2O is a stable, non-radioactive isotope that is indistinguishable from normal water. A target of 1–2% enrichment is achieved during a one-week priming stage (50 ml of D2O 3x/d = 150 ml/d) and maintained for three weeks (50 ml of D2O 2x/d = 100 ml/d) as we have previously performed.

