Minors are not included because the cost-benefit ratio is not clear and therefore inappropriate for this study.

- e) **State if any of the subjects are students, employees, or laboratory personnel. They should be presented with the same written informed consent. If compensation is allowed, they should also receive it.**

If any of the subjects are students, employees, or laboratory personnel they will be presented with the same written informed consent and compensation.

- f) **Describe how potential subjects will be identified for recruitment (e.g., chart review, referral from individual's treating physician, those individuals answering an ad). How will potential participants learn about the research and how will they be recruited (e.g., flyer, email, web posting, telephone, etc.)? Attach recruitment materials in the Attachment Section (#16). Important to remember: potential subjects may not be contacted before IRB approval.**

Potential subjects will be recruited initially from the Colorado State and Fort Collins community via email, electronic, newspaper, radio, or bulletin advertisements. Colorado State employees, local physicians and interested participants may be emailed for recruitment and communication purposes. Physicians will be contacted so if they have prediabetic patients they can be informed of the research study which includes standard care treatment options (i.e., physical activity and metformin). Text for advertisements will be obtained from the attached flyer. Information for local physicians is also attached.

- g) **If applicable, provide rationale for the inclusion of healthy volunteers in this study. Specify any risks to which these healthy volunteers may possibly be exposed. Specify the measures being taken to minimize the risks and the chance of harm to these volunteers.**

We will include healthy volunteers to compare to individuals at risk for T2D. No additional risks are known for healthy individuals compared to those at risk for T2D. Healthy individuals will not perform the intervention.

---

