**Identify inclusion criteria.**

We plan to recruit 120 men and women with an estimation that 15-25% of participants will not qualify (i.e., screen out) and 15-25% of participants will not complete the study (i.e. drop out). We plan to complete the study in 60 men and women aged >55 years who are prediabetic defined as impaired fasting glucose (100 to 126 mg/dl), HbA1c (5.7-6.4%), family history of type 2 diabetes, and/or impaired glucose tolerance defined as 2 hour postprandial blood glucose of 140 to 200 mg/dl. Participants will be eligible if they meet any 1 of these criteria.

10 healthy participants will be recruited who are 18-45 years old who have normal glucose values (fasting glucose <100mg/dl, HbA1c <5.7%, 2 hour postprandial blood glucose <140 mg/dl) and no family history of T2D.

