**Identify exclusion criteria.**

Medications contraindicated with Metformin (Dofetilide, Lamotrigine, Pegvisomant, Somatropin, Trimethoprim, Trospium, Gatifloxacin, Cephalexin, Cimetidine, Dalfampridine)  
Recent (less than 6 weeks) or planned imaging that requires IV contrast  
Renal failure, creatinine  $\geq$  1.3 mg/dL in men or  $\geq$  1.2 mg/dL in women  
ALT levels exceed 52 IU/L  
Heart, Kidney or Liver Disease  
Type I or Type II Diabetes  
Anti-coagulant therapy (warfarin/heparin)  
Lung/respiratory dysfunction  
Medications affecting primary outcomes  
Lactose Intolerant  
Tobacco Use  
Heavy Alcohol Use  
Cancer  
Lidocaine Allergy  
EKG that is nondiagnostic for ischemia, such as: Complete Left bundle branch block or nonspecific Intraventricular conduction delay with ST/T changes; LVH with significant ST changes; Wolff-Parkison-White syndrome; ventricular pacemaker; digoxin therapy with greater than 1 mm ST depression or  
Arrhythmias, such as: Uncontrolled rate in atrial fibrillation; nonsustained ventricular tachycardia.

- i) **Describe your screening procedures. Attach your screening document(s) (e.g., health history questionnaire) in the Attachment Section (#16).**

Blood draw for chemistry panel, health questionnaire, medical history questionnaire, oral glucose tolerance test, resting and exercise EC.

- j) **Describe how you will be cognizant of other protocols in which subjects might be participating. Please explain if subjects will be participating in more than one study.**

Subjects will be instructed to communicate with investigators should they consider or begin to participate in other studies. Subjects participating in studies that may confound the results of the present investigation will be asked to withdraw from the the present investigation.

- k) **Compensation. Explain the amount and schedule of compensation, if any, that will be paid for participation in the study. Compensation includes food, gift cards, money, tokens, etc. Include provisions for prorating payment, if applicable. Compensation should be prorated if several activities are involved for different time periods (e.g., \$10 for session #1, and \$10 for session #2).**

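### No stated limit on habitual exercise and no activity measure required of every randomised participant, so training-dependent effects may be attenuated

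*Combined protocol and SAP*

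**What the plan says.** **Entry.** Section 8h admits adults over 55 with any one of four features: raised fasting glucose, raised HbA1c, impaired glucose tolerance or a family history of type 2 diabetes. "Participants will be eligible if they meet any 1 of these criteria". The exclusions cover interacting drugs, organ disease, diabetes, tobacco, heavy alcohol use, cancer and ECG findings. The nearest item is "Medications affecting primary outcomes", which concerns drugs. The Study Overview in section 2a summarises screening as: "Prediabetic participants will be screened to eliminate those lactose intolerant, medications known to affect the primary outcomes, medications or recent procedures contraindicated with metformin", and also removes those who are not prediabetic. None of these places mentions current exercise or fitness.

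**Screening procedures (8i).** "Blood draw for chemistry panel, health questionnaire, medical history questionnaire, oral glucose tolerance test, resting and exercise EC". No activity measure is named.

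**Where activity is recorded.** The questionnaire belongs to the optional counselling study: "If the subjects wish to participate they will complete questionnaires to measure sociodemographic information, physical activity" and related items. An activity log is also kept during CGM wear (Detailed Procedures). CGM is optional too, and section 8a plans it for 20 prediabetic participants against 60 completers.

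**Fitness.** Every participant has a graded exercise test with VO2max among the first assessments. No threshold is attached to it.

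**Programme.** Three sessions a week for 12 weeks, each with a 15-minute warm-up at 60% of maximum heart rate followed by "workout stages (30 min, progression from 65 to 85% of max heart rate by wk 5".

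**Balance and analysis.** Groups are to be matched on subject characteristics that are not named. The Statistical Plan gives a Treatment Group by Time ANOVA and unpaired t-tests on change, without covariates.

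**The concern.** Section 1 asks whether protein enhances the response to training and whether it overcomes a blunting of that response by metformin. Someone who already trains at about the programme's load has less response left to enhance or to blunt. As written, a regular exerciser aged over 55 with a family history of diabetes can be randomised.

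Two things follow. First, contrasts that depend on the size of the training response shrink towards zero in proportion to the share of such people. A finding that metformin does not blunt, or that protein adds nothing, could then partly reflect who was enrolled. Second, with small groups the trained participants may fall unevenly by chance. Respirometry and western blots are done before and after training, so fixed baseline differences drop out of their change scores. Isotope incorporation is measured only after training, so it has no baseline of its own and any imbalance goes directly into the group comparison. This is the outcome that addresses the mitochondrial protein synthesis hypothesis.

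**Working it through.** The documents give no power, effect size or SD, so there is no power figure to reproduce. The only size figure is 60 completers from 120 recruited. It is met if both losses are taken at 25% and added: 120 × (1 − 0.25 − 0.25) = 60.

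**Inputs from the documents**
- 60 completers in four groups (sections 8h and 2a). The allocation ratio is not stated; if equal, 60 / 4 = 15 per group, or 30 v 30 when one factor is compared across the other.
- Significance level 0.05 (Statistical Plan), taken as two-sided.
- Weekly load: (15 + 30) × 3 = 135 minutes, of which 15 × 3 = 45 are warm-up and 30 × 3 = 90 are the workout stage.

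**Assumptions, not in the documents**
- A share f of participants is already trained: 10%, 20% or 30%.
- Trained participants keep a fraction k of the treatment effect: k = 0 or k = 0.5.
- The effect d in untrained participants is the one that would give 80% power if f were zero.

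**Step 1: reference effect.** Solving noncentral-t power for 80% gives d = 1.060 at 15 v 15 and d = 0.736 at 30 v 30.

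**Step 2: diluted effect.** The average effect is d × [1 − f(1 − k)]. For f = 20% at 15 v 15:
- k = 0: 1.060 × 0.80 = 0.848
- k = 0.5: 1.060 × 0.90 = 0.954

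**Step 3: power at the diluted effect.** To the nearest per cent the results are the same for 15 v 15 and 30 v 30.

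| Share trained | No effect in trained | Half effect in trained |
|---|---|---|
| 0% | 80% | 80% |
| 10% | 71% | 76% |
| 20% | 61% | 71% |
| 30% | 50% | 66% |

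With no effect in the trained, the sample size needed to recover 80% rises by about 1/(1 − f)²: 1.23, 1.56 and 2.04 times.

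**Step 4: added variance (a harsher case).** Suppose also that the training response averages 1 SD in the untrained and zero in the trained. The SD then grows by √[1 + f(1 − f)], and with no effect in the trained, power is 68%, 55% and 43%.

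**Step 5: chance imbalance.** If training status plays no part in the matching, the difference in the trained share between two groups of 15 has standard deviation √[2f(1 − f)/15]. At f = 20% this is √(0.32/15) = 0.146, about two people in 15 (0.146 × 15 = 2.2). At 10% and 30% it is 0.110 and 0.167.

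**The case against.** Several points on the other side are sound.

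- **Some information exists for everyone.** Baseline VO2max is an objective fitness measure and could be matched on or adjusted for. A reader might infer that training status is measured only in the counselling volunteers and cannot be handled otherwise. The documents do not support that: CGM participants keep an activity log, and all participants have VO2max. What stands is that no activity measure is required of all, and that VO2max, a proxy, is given no such role.
- **Not every effect is diluted.** A reader might infer that all contrasts shrink. The background in section 3a describes direct inhibition of mitochondrial respiration by metformin, and nothing says this vanishes in trained people. Isotope labelling runs over the last four weeks while sessions and drinks continue, so a protein effect there need not require an untrained participant.
- **The share trained is unknown.** Recruitment is broader than a campus: "Potential subjects will be recruited initially from the Colorado State and Fort Collins community", with local physicians also approached. Nothing shows that trained volunteers will be common.
- **Intensity is relative.** It is set against each person's maximum heart rate, which softens the problem without removing it.
- **Unseen attachments.** The medical and pre-screening forms and a separate GCP protocol are listed but not shown, and may ask about exercise. Even so, no stated criterion uses the answer.
- **Broad entry is legitimate.** Randomisation protects against systematic bias. It does not prevent dilution or chance imbalance in small groups.

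**Conclusion.** The concern holds in limited form. No stated criterion limits habitual aerobic exercise, no activity measure is required of every randomised participant, and the one fitness measure taken in all has no stated use in eligibility, matching or analysis. Training-dependent effects may be attenuated, and the post-only isotope outcome is exposed to chance imbalance.

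The size cannot be fixed from the documents. With 10% to 30% already trained, power falls from 80% to between 71% and 50% if they show no effect, or to between 76% and 66% if they keep half. The share, the retained fraction and the 80% starting point are all assumptions. The zero-effect column and the added-variance case are pessimistic settings and should not be read as forecasts.

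**What to change.** 1. Give the short IPAQ form, already listed under Attachments (section 16), to every prediabetic participant at screening, whether or not they join the counselling study.
2. In section 2a, name screening activity and baseline VO2max among the characteristics matched at randomisation.
3. In the Statistical Plan, include both as covariates for the training outcomes, above all for isotope incorporation. For change in VO2max, the baseline value serves as the usual baseline covariate.

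The cost is one short form per participant and one or two degrees of freedom: with 60 completers in four groups, 60 − 4 = 56 residual degrees of freedom become 54 with two covariates.

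Adjustment improves balance and precision but does not restore an effect that is absent in trained people. If the investigators want to address dilution itself, they could limit current structured training at entry. Such a limit should be defined by intensity as well as minutes, because 45 of the programme's 135 weekly minutes are warm-up, and a minutes-only rule would also exclude people for whom the programme is still a step up. Its cost is slower recruitment and a narrower population, so it is the investigators' choice. If the unseen forms already record exercise, the protocol should say so and state how the answer is used.
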